**ALIVE Study** 

21st January 2022

The investigators will ensure that all study personnel including the study physicians involved in the study will respect the confidentiality of any information about the participants of the trial.

### 10.2 ADDITIONAL CONSIDERATIONS

#### **Trial site selection**

All three sites offer a combination of expertise, complementary prevalence of the three species of STH under study and laboratory facilities to conduct studies of this type:

Bahir Dar University, Amhara, Ethiopia: this site has been able to identify high prevalence of infections with hookworms and *S. stercoralis* in their area of influence and has been leading clinical research on the topic (61).

KEMRI, Nairobi, Kenya is the reference institution in the country with long-standing experience and expertise in STH and a key role in mapping the distribution of these infections; high prevalence of hookworms and *T. trichiura* have been detected in the study area as part of ongoing studies (62–64).

FM-CISM, Manhiça, Mozambique: The last national survey of STH distribution in Mozambique was conducted in 2008, showing a 53.5% prevalence for STH (65). The estimated prevalence of STH in Maputo Province where the clinical trial will be conducted was 37.1% and the prevalence of *T. trichiura* was 45%. Preliminary data from a pilot study conducted in Manhiça showed 8% prevalence of *S. stercoralis* in the study area ([name], unpublished data).

Version 4.0 21st January 2022

ALIVE Study

# 10.3 ABBREVIATIONS

AE	Adverse Event		
ALB	Albendazole		
ATP	According-To-Protocol		
СоА	Certificate of Analysis		
CRF	Case Report Form		
CRO	Contract Research Organisation		
DSMB	Data Safety Management Board		
eCRF	Electronic Case Report Forms		
EDCTP	European and Developing Countries Clinical Trials Partnership		
EMA	European Medicines Agency		
ERR	Egg Reduction Rate		
FDC	Fixed Dose Co-formulation		
GBD	Global Burden of Disease		
GCP	Good Clinical Practice		
GLP	Good Laboratory Practices		
GMP	Good Manufacturing Practices		
IB	Investigator's Brochure		
ICH	International Conference on Harmonisation		
IMP	Investigational Medicinal Product		
IF	Investigators Folder		
ITT	Intention-To-Treat		
IVM	Ivermectin		
NTDs	Neglected Tropical Diseases		
PC	Preventive Chemotherapy		
PCR	Polymerase Chain Reaction (real-time)		
PI	Principal Investigator		
PSAC	Pre-School Age Children		
QA	Quality Assurance		
QC	Quality Control		
SOA	Schedule Of Activities		
SAC	School-Age Children		
SAE	Serious Adverse Event		
SOP	Standard Operating Procedure		
STH	Soil Transmitted Helminths		
SUSAR	Suspected unexpected serious adverse reactions		
WHO	World Health Organisation		
YLD	YED Years lived with disability		

Version 4.0 21st January 2022

**ALIVE Study** 

### 10.4 PROTOCOL AMENDMENT HISTORY

The table below is intended to capture changes of regulatory approved versions of the protocol, including a description of the change and rationale.

Version	Date	Description of Change
v1.4	20 th February 2019	Original
		(based on the clinical trial proposal submitted to the EDCTP on
		the 31 st of October 2017 for grant approval)
V2.1	20 th May 2020	Changes of the trial design from a phase III to an adaptive phase II/III clinical trial. Thus, the safety and pharmacokinetics of the
		FDC is tested in the phase II component prior to testing its
		efficacy in the phase III component of the trial. The primary
		endpoint of the phase III component will now be CR for T.
		trichiura.
		General typos and administrative corrections.
V3.0	25 th August 2021	Phase II component
		A description of the procedures for staged enrolment and
		DSMB clearance has been included. Recruitment will
		start with the weight group 1 and only after safety data
		has been reviewed by the DSMB and clearance provided
		recruitment in the following weight group will be
		initiated.
		
 
Secondary objective and endpoints updated to include efficacy of FDC in paediatric population.
 

		PK section updated to include population PK. Two
		sampling times per participant included covering two
		different post-dosing ranges from 1 to 7 hours post-
		administration and from 8 to 72 hours post-
		administration. The overall sampling times describe the
		entire pharmacokinetic profile for the two drugs (IVM
		and ALB) for each of the 3 groups of body weight [23-
		<30kg, 30-45kg and 15-23kg].
		Phase II- Phase III component
		
 
Stopping rules have been clarified. Rules for dose
 

		escalation in phase II and for the progression from phase
		II to phase III have been included as well as stopping rules
		for further dosing and trial termination.
		Rescue medication section updated.
		Guidance provided to the site concerning potentially
		interacting drugs: current use of warfarin at screening
		has been included exclusion criteria.
		The Schedule of Activities has been updated to include
		the possibility of unscheduled visits.

Version 4.0

		Version 4.
ALIVE Stud	У	21st January 202
		
 
Pregnancy reporting requirements have been included.
 

		
 
IMP storage requirements have been updated.
 

		
 
Study monitor contact details updated.
 

		
 
General typos and minor inconsistencies corrected.
 

V4.0	21 st January 2022	Schedule of Assessments adjusted to reflect that
		haematuria strip test is done for Schistosoma, no
		measurement of weight/height is required at withdrawal
		visit, pre-screening activities starting 3 months prior to
		screening, acceptability in phase II only applies for FDC
		arms.
		
 
Typographical error adjusted in the PK section: FDCx3
 

		arm has an additional PK time pre-dose Day 2 (instead of
		Day 3), before the last intake of the study medication.
		
 
Section 9 Statistical considerations updated to adjust an inconsistency in the treatment arms.
 

		
 
Consent process allowed to be performed up to 3 months prior to screening.
 

		
 
Randomization envelopes allowed to be opened by responsible on the day prior to baseline visit.
 

Version 4.0 21st January 2022

1. INTRODUCTION

The purpose of this Statistical Analysis Plan (SAP) is to define the outcome variables, statistical methods, and analysis strategies to address the study's objectives in Adaptive phase II/III Single-Blinded, Randomized, Multi-Centre, Parallel-Group, Active-Controlled, Superiority Study to Evaluate the Safety and Efficacy of a Single Day or 3-day Single Dose of an ALBENDAZOLE-IVERMECTIN Co-formulation vs ALBENDAZOLE for the Treatment of Soil-Transmitted Helminth Infections (*Trichuris trichiura*, hookworm, *Strongyloides stercoralis*) in Paediatric and Young Adult Population (ALIVE Study).

2. STUDY OBJECTIVES AND OUTCOMES

2.1 Objectives

2.1.1 Phase II component

2.1.1.1 Primary objective

To evaluate the **safety** of the FDC as a single dose or three-dose regimen for the treatment of *T. trichiura* in paediatric and young adult population.

2.1.1.2 Secondary objectives

- 1. To evaluate the efficacy of FDC against *T. trichiura* in paediatric population.
- 2. To evaluate the efficacy of FDC against hookworms and *S. stercoralis* in those co-infected with species concomitantly to their infections with *T. trichiura*.
- 3. To describe the extent of albendazole and ivermectin exposure in different weight strata.
- 4. To evaluate the acceptability/palatability of the FDC 400mg-18mg and 400mg-9mg.

2.1.2 Phase III component

2.1.2.1 Primary objective

To evaluate the efficacy of the FDC as a single dose or 3-day single dose regimen compared to the standard single dose regimen of ALB (400 mg) for the treatment of *T. trichiura* in paediatric and young adult population.

2.1.2.2 Secondary objectives

- 1. To evaluate the **efficacy** of the FDC as a single dose or 3-day single dose regimen for the treatment of hookworm and *S. stercoralis*.
- 2. To evaluate the safety of the FDC as a single dose or 3-day dose regimen for the treatment of *T. trichiura*, hookworm and *S. stercoralis*.
- 3. To evaluate the performance of PCR in calculating the primary outcome measurement (efficacy) compared to an egg counting method (Kato-Katz).
- 4. To evaluate the frequency of known ALB resistant alleles in hookworm and *T. trichiura* in the three treatment arms before and after treatment.

2.1.2.3 Exploratory objectives

- 1. To assess the efficacy of the FDC against *A. lumbricoides* in co-infected participants compared to single dose ALB in participants co-infected with this STH.
- 2. To describe the efficacy of the FDC in the prevalence of scabies compared to single dose ALB 400 mg.
- 3. To evaluate the efficacy of the FDC in co-infected participants compared to single dose ALB in participants co-infected with STH.

2.2 Outcomes

2.2.1 Primary outcome

Safety evaluations: Safety evaluations and measurements, including adverse events (AEs), vital signs, physical examination, weight, height and BMI will be assessed from the time of signing the informed consent through to post-treatment follow-up visit. To evaluate safety, participants will be evaluated as detailed in the schedule of visits (Table 1 and Table 2). All AEs during all study visits, will be noted in the CRF for each participant. A close surveillance, 3 hours post-treatment, will be conducted each day a participant receives treatment.

Any clinically significant abnormalities persisting at the end of the study will be followed up by the study physician until resolution or until a clinically stable endpoint is reached.

A Data Safety Monitoring Board (DSMB) will monitor the ongoing safety of the participants during the study.

Efficacy evaluation: Anti-helminthic primary efficacy, measured by cure rate will be determined by analysing a stool sample taken 21(+/-7) days after completing treatment with Kato Katz, Baermann. [1,2]

Cure is defined as absence of the species of STH in participants who had a positive egg count and/or larva for that STH species at baseline. Cure rate (CR) is defined as the proportion of individuals cured (absence of any egg and/or larva) to the total of those infected at baseline with each particular species of STH.

Table 1. Schedule of Activities Phase II Component (KENYA only)

	1							r	
Procedures	Study Visit 0 Screening Day -7 to -1	Study Visit 1 Enrolment/ Baseline Day 0	Study Visit 2 Day 1	Study Visit 3 Day 2	Study Visit 4 Day 3	Study Visit 5 Day 7	Study Visit 6 Day 21+/-7 day post treatment	Unscheduled	Withdrawal
Informed consent ¹	Х								
Informed assent ²	Х								
Stool collection kit delivered	Х						Х		
Stool collection ³	Х						Х		Х
Stool analysis (Baermann and Kato-Katz) ⁴	х						Х		х
Inclusion and Exclusion criteria	Х	Х							
Demographics ⁵	Х								
Physical exam ⁶	Х	Х					Х	Х	Х
Vital signs ⁷	Х	Х	Х	Х	Х	Х	Х	Х	Х
Height	Х	Х							
Weight	Х	Х							
Urine Pregnancy test ⁸	Х								
Haematuria strip test as proxy for Schistosoma h	х								
Randomization and treatment assignation		х							
Study drug administration		X ⁹	X ¹⁰	¹¹ X					
Acceptability questionnaire Arm 1 (ALB)									
Acceptability questionnaire Arm 2 (FDCx1)		х							
Acceptability questionnaire Arm (FDCx3)				х					
PK blood sampling		X ¹²	XI	XI					
Study drug accountability		Х	Х	Х			Х		Х
Concomitant medication & disease review	х	х	х	х	Х	х	Х	Х	x
Adverse event monitoring ¹³	Х	Х	Х	Х	Х	Х	Х	Х	Х
Complete Case Report Form (CRF)	х	х	х	х	Х	Х	Х	Х	х

¹ Informed consent will be obtained from parents or guardians of all participants <18years

⁴ Lab tests will be performed on a fresh stool sample collected <24 hours before examination.

² Assent to participate in the trial will be obtained from participants 12-17 years old.

³ A stool collection kit will be provided to participants for the collection of stool samples after providing assent and consent. The stool should be collected <24 h before examination for eligibility check. An aliquot of the collected stool sample will be stored for QC by PCR to confirm microscopic results from Kato-Katz and Baermann test if microscopy positive at screening and for all follow-up stool samples. All samples will be tested at site. Should technical issues arise or in case of discrepancy in results, an aliquot of the stool sample will be tested abroad for QC purposes.

⁵ Age, Date of Birth, Sex, Participant ID, Guardian relationship, age and contact details

⁶ Physical exam should include clinical diagnosis of scabies (rush/lesions on skin) before and after treatment. During unscheduled visits Physical exam will be performed only if necessary.

⁷ Vital signs should Include heart rate, respiration rate, body temperature and blood pressure.

⁸ A urine test kit will be provided in order to collect a urine sample from which will be examined by a haematuria strip test as a proxy for *Schistosoma* eggs and to confirm negative pregnancy test for female participants ≥12 years old or post-menarche.

⁹ Treatment Day (D)0. For all participants in Arms 1, 2 and 3. Treatment dose will be given under direct supervision.

¹⁰ Treatment D1. Only for participants in treatment Arm 3. Close observation for 3 hours post-treatment for safety evaluations

¹¹ Treatment D2. Only for participants in treatment Arm 3. Close observation for 3 hours post-treatment for safety evaluations.

¹² Population PK (2 timepoints per participant). for ALB arm at 1, 2, 3, 4, 5, 6, 7, 8, or 24h; for the single dose FDC arm at 1, 2, 3, 4, 5, 6, 7, 8, 24h, 48 or 72h; for three-dose FDC arm at pre-dose Day 3, 1, 2, 3, 4, 5, 6, 7, 8, 24h, 48 or 72h post-administration.

¹³ Adverse events will be assessed by direct observations of the study physician, or reported by the participant or parent/guardian.

Procedures	Pre-screening (up to 3 months prior scree.)	Study Visit 0 Screening Day -7 to -1	Study Visit 1 Enrolment/Ba seline Dav 0	Study Visit 2 Day 1	Study Visit 3 Day 2	Study Visit 4 Day 3	Study Visit 5 Day 7	Study Visit 6 Day 21+/-7 day post treatment	Unscheduled	Withdrawal
Informed consent ¹⁴	Х	Х								
Informed assent ¹⁵	Х	Х								
Stool collection kit delivered		Х						Х		
Stool collection ¹⁶		Х						Х		Х
Stool analysis (Baermann and Kato-Katz) ¹⁷		Х						Х		Х
Inclusion and Exclusion criteria		Х	Х							
Demographics ¹⁸		Х								
Physical exam ¹⁹		Х	Х					Х	Х	Х
Vital signs ²⁰		Х	Х	Х	Х	Х	Х	Х	Х	Х
Height		Х	Х							
Weight		Х	Х							
Urine Pregnancy test ²¹		Х								
Haematuria Strip test as proxy for Schistosoma ^h		х								
Serum HIV test ²²		Х	Х							
Randomization and treatment assignation			Х							
Study drug administration			X ²³	X ²⁴	X ²⁵					
Study drug accountability			Х	Х	Х			Х		Х
Concomitant medication & disease review		Х	Х	Х	Х	Х	Х	Х	Х	Х
Adverse event monitoring ²⁶		Х	Х	Х	Х	Х	Х	Х	Х	Х
Complete Case Report Form (CRF)		Х	Х	Х	Х	Х	Х	Х	Х	Х

Table 2. Schedule of Activities Phase III component (all sites)

2.2.2 Secondary outcomes

Treatment efficacy: Anti-helminthic efficacy, measured through egg reduction rate (ERR), will be determined by analysing a stool sample taken 21(+/-7) days after completing treatment with Kato Katz[2]. Egg reduction rate (ERR) will be calculated by using geometric means, calculated for hookworms, *T. trichiura* and *A. lumbricoides*. In addition, Anti-helminthic efficacy, measured by cure

¹⁸ Age, Date of Birth, Sex, Participant ID, Guardian relationship, age and contact details

²⁰ Vital signs should Include heart rate, respiration rate, body temperature and blood pressure.

¹⁴ Informed consent will be obtained from parents or guardians of all participants <18years. Informed consent/assent can be performed up to 3 months prior to screening visit as part of the pre-screening activities OR during screening visit

 $^{^{\}rm 15}$ Assent to participate in the trial will be obtained from participants 12-17 years old.

¹⁶ A stool collection kit will be provided to participants for the collection of stool samples after providing assent and consent. The stool should be collected <24 h before examination for eligibility check. An aliquot of the collected stool sample will be stored for QC by PCR to confirm microscopic results from Kato-Katz and Baermann test if microscopy positive at screening and for all follow-up stool samples. All samples will be tested at site. Should technical issues arise or in case of discrepancy in results, an aliquot of the stool sample will be tested abroad for QC purposes.

¹⁷ Lab tests will be performed on a fresh stool sample collected <24 hours before examination.

¹⁹ Physical exam should include clinical diagnosis of scabies (rush/lesions on skin) before and after treatment. During unscheduled visits Physical exam will be performed only if necessary.

²¹ A urine test kit will be provided in order to collect urine sample from all participants which will be examined by haematuria strip test as a proxy *for* Schistosoma eggs and to confirm negative pregnancy test for female participants \geq 12 years old or post-menarche.

²² Serum HIV test will be offered only to eligible participants at the Manhiça site in Mozambique because of high HIV prevalence.

²³ Treatment Day 0. For all participants in Arms 1, 2 and 3. Treatment dose will be given under direct supervision.

²⁴ Treatment Day 1. Only for participants in treatment Arm 3. Close observation for 3 hours post-treatment for safety evaluations.

²⁵ Treatment Day 2. Only for participants in treatment Arm 3. Close observation for 3 hours post-treatment for safety evaluations.

²⁶ Adverse events will be assessed by direct observations of the study physician, or reported by the participant or parent/guardian.

rate will be determined by analysing a stool sample taken 21(+/-7) days after completing treatment with qPCR.

At pre- and post-treatment visits a duplicate Kato-Katz test will be performed on a fresh stool sample collected <24 hours before examination. Baermann method will also be performed in parallel to Kato-Katz for the search of *S. stercoralis*. Evaluation by qPCR will be performed in pre- and post-treatment samples.

Pharmacokinetic outcome measures (only phase II): Two blood samples for population PK analysis will be collected for every participant by finger prick using the mitra devices [3] in the phase II component to adjust a population pharmacokinetic model. Additionally, a NCA will be performed to obtain (Cmax), time to reach Cmax (Tmax) and area under the curve (AUC) of ALB and IVM. A complete description of the pk analysis can be found in the statistical analysis plan for pharmacokinetics.

Participant acceptability/palatability outcome measures (only phase II):

Facial hedonic scale and implied numerical rating scale (NRS) will be included in the Phase II component of the trial to measure attributes for the FDC orodispersible formulation in terms of taste, aftertaste; mouth feel; smell; time needed to dissolve/disperse (duration of administration). Secondary aspects will include visual aspects: embossing, surface aspects and colour. Refer to the protocol Section 9.5.2 for details.

Resistance: Whole genome sequencing, next-generation DNA sequencing and omic approaches will be used to assess underlying factors associated with low treatment response including assessment and evaluation of new protocols for sample processing and sequencing.

3. STUDY DESIGN

3.1 Design

Adaptive phase II/III trial to compare safety and efficacy of the active control arm (current standard of care) against 2 experimental arms.

Phase II component

Uni-centric, 3-arm, parallel, open-label, randomised, phase II trial to determine the safety and tolerability of FDC in paediatric population in different weight strata. Stratification by weight thus recruiting sequentially for safety and tolerability.

- Group 1 (38 participants): with body weight of [23-<30) Kg will receive 300-391 μ g/Kg (FDC 400mg-9mg) or ALB.
- Group 2 (38 participants): with body weight of [30-45] Kg will receive 400-600 μg/Kg (FDC 400mg-18mg) or ALB.
- Group 3 (50 participants): with body weight of [15-23) Kg will receive 391-600 $\mu g/Kg$ (FDC 400mg-9mg) or ALB.

ISGIODAI Barcelona Institute for Global Health

[figure not shown]

Figure 2. Phase II design (Kenya)

Phase III component

A Single-Blinded, Randomized, Multi-Centre, Parallel-Group, Active-Controlled, Superiority Study to Evaluate the Efficacy and Safety of a Single Day or 3-day Single Dose of FDC for the treatment of *Trichuris trichiura*, hookworm, *Strongyloides stercoralis* in paediatric and young adult population.

- a. Arm 1: Single dose of a tablet of ALB 400 mg (active control arm)
- b. Arm 2: Single dose of a tablet of FDC 400mg-18mg (≥45 kg of body weight at baseline) or 400mg-9mg (<45 kg of body weight at baseline).
- c. Arm 3: Daily dose of a tablet of FDC 400mg-18mg (≥45 kg of body weight at baseline) or 400mg-9mg for 3 days (<45 kg of body weight at baseline).

[figure not shown]

Figure 3. phase III design (Kenya, Ethiopia, Mozambique)

3.2 Trial sites

This study will be conducted in primary and secondary schools in Kenya (phase II and phase III), Ethiopia (phase III) and Mozambique (phase III).

3.3 Treatment

Phase II component

Participants will be randomly allocated with unequal probability to receive either:

Treatment Arm 1: Single dose of a tablet of ALB

Treatment Arm 2: Single dose of a tablet of FDC

Treatment Arm 3: Daily dose of a tablet of FDC for 3 days.

and will be recruited by μ g/Kg of IVM to be received in a sequential manner starting from Group 1 through to Group 3 as shown below:

- Group 1: receiving 300-391 μg/Kg or ALB 400mg- 38 participants (body weight: 23-<30 Kg) will be recruited in this group. (FDC 400mg-9mg).
- Group 2: receiving 400-600 µg/Kg or ALB 400mg− 38 participants (body weight: 30-45 Kg) will be recruited in this group. (Participants <45 kg: FDC of 400mg ALB-9mg IVM, participants ≥45 kg: FDC of 400mg ALB-18mg IVM).
- Group 3: receiving 391-600 μg/Kg or ALB 400mg- 50 participants (body weight: 15-23 Kg) will be recruited in this group. (FDC 400mg-9mg).

Phase III Component

Participants will be randomly allocated with unequal probability (Arm 1 p=0.2, Arm2 p=0.4, Arm3 p=0.4), according to the specific expected cure rate by specie, to receive either:

Treatment Arm 1: Single dose of a tablet of ALB 400 mg (active control arm).

- Treatment Arm 2: Single dose of a tablet of FDC 400mg-18mg or 400mg-9mg.
 - For participants <45 kg of body weight at baseline: FDC of 400mg ALB-9mg IVM.

◦ For participants ≥45 kg of body weight at baseline: FDC of 400mg ALB-18mg IVM.

Treatment Arm 3: Daily dose of a tablet of FDC 400mg-18mg or 400mg-9mg for 3 days.

- For participants <45 kg of body weight at baseline: FDC of 400mg ALB-9mg IVM.
- For participants ≥45 kg of body weight at baseline: FDC of 400mg ALB-18mg IVM.

3.4 Randomisation

In the phase II component, participants with *T. trichiura* infection (confirmed by Kato-Katz technique in a fresh stool sample) will be enrolled in a sequential manner per weight group in order to administer the desired dose, starting from 300-391 μ g/kg ivermectin. Participants in the phase II trial will be stratified in different weight groups: Group 1 (23-<30 kg) 38 participants, group 2 (30-45 kg) 38 participants and group 3 (15-23 kg) 50 participants in order to gradually increase the dose of ivermectin in the FDC. Then, participants will be allocated by simple randomization to one of the three study arms with unequal probability (ALB: p=0.2, n=26; FDCx1: p=0.4, n=50; FDCx3: p=0.4, n=50) In the phase III component, allocation of participants to study arms will be done by block randomization and stratified by STH species. We will ensure balanced allocation to the three arms in the three study countries. Treatment allocation for each study participant will be concealed in opaque sealed envelopes that will be opened only after enrolment. Study participants will be assigned a unique study number linked to the allocated treatment group. Participants will be randomly allocated with unequal probability, according to the specific expected cure rate of each species.

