**Method of Allocation** 

In the phase II component, participants with *T. trichiura* infection (confirmed by Kato-Katz technique in a fresh stool sample) will be enrolled in a sequential manner per weight group in order to administer the desired dose, starting from 300-391  $\mu$ g/kg ivermectin. Participants in the phase II trial will be stratified in different weight groups: Group 1 (23-<30 kg) 38 participants, group 2 (30-45 kg) 38 participants and group 3 (15-23 kg) 50 participants in order to gradually increase the dose of ivermectin in the FDC. Then, participants will be allocated by simple randomization to one of the three study arms (ALB, FDCx1 and FDCx3).

In the phase III component, allocation of participants to study arms will be done by block randomization and stratified by STH species. We will ensure balanced allocation to the three arms in the three study countries. Treatment allocation for each study participant will be concealed in opaque sealed envelopes that will be opened only after enrolment. Study participants will be assigned a unique study number linked to the allocated treatment group. The allocation ratio for the three study arms will be 1:1:1.

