4. ANALYSIS POPULATIONS

4.1 Study population data sets

Safety population

The safety analysis will be based on the intention-to-treat (ITT) population, defined as all participants who were randomized in the trial.

Efficacy population

The efficacy analysis will be based on the ITT population. For the handling of missing data, the worstcase scenario will be considered, considering all individuals without efficacy data as treatment failures. **Population PK analysis (phase II)** A complete description of the pk analysis can be found in the statistical analysis plan for pharmacokinetics.

For population pharmacokinetic analysis, the 126 participants included in the 3 arms of phase II (26 in arm 1, and 50 in the arms 2 and 3) will be randomly assigned to different subgroups (7 subgroups for arm 1, and 10 subgroups for arm 2 and 3) with different sampling times (2 blood samples per subgroup for arm 1 and 2, and 2 blood samples plus predose on Day 2 per subgroup for arm 3). The two sampling times has been randomly obtained from two different post-dosing ranges covering from 1 to 7 hours (range I) and from 8 to 72 hours (range II). Thus, the overall sampling times describes the entire pharmacokinetic profile for the two drugs (Ivermectin and Albendazole) for each of the 3 groups of body weight (Group 1: 23-30kg, Group 2: 30-45kg, and Group 3:15-23kg).

For the random assignment of the blood capilar extractions (with Mitra (40) Clamshell), a randomization of the times of PK extraction (9 points for arm 1 and 11 and 12 points for arms 2 and 3

respectively) will be carried out carried out for each arm of treatment: [+1h, +2h, +3h, +4h, +5h, +6h, +7h, +8h and +24h] for the arm 1 (albendazole treatment); and [+1h, +2h, +3h, +4h, +5h, +6h, +7h, +8h, +24h, +48h and +72h] for the arm 2 (coadministration IVM+Albendazole); and [baseline preadministration on Day 2 and +1h, +2h, +3h, +4h, +5h, +6h, +7h, +8h, +24h, +48h and +72h] for arm 3 (coadministration IVM+Albendazole)x3 consecutive days)..

For Arm 1 (albendazole treatment), the 9 points (+1h, +2h, +3h, +4h, +5h, +6h, +7h, +8h and +24h) has been divided in 2 groups:

i) One group of 5 points comprising the points from +1h until +5h

ii) One group of 4 points comprising the points from +6h until +24h

For assigning the 2 points we randomize 1 time from each group

For Arm 1 (5 subgroups of 4 participants + 2 subgroups of 3 participants):

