SubGroup 1 (n=4): +3h, +6h SubGroup 2 (n=4): +4h, +24h SubGroup 3 (n=4): +2h, +8h SubGroup 4 (n=4): +5h, +7h SubGroup 5 (n=4): +1h, +7h SubGroup 6 (n=3): +2h, +24h SubGroup 7 (n=3): +4h, +8h

For Arm 2 (albendazole + ivermectin treatment), the 11 points (+1h, +2h, +3h, +4h, +5h, +6h, +7h, +8h, +24h, +48h, +72h) has been divided in 2 groups:

i) One group of 6 points comprising the points from +1h until +6h

ii) One group of 5 points comprising the points from +7h until +72h

For assigning the 2 points we randomize 1 time from each group For Arm 2 (10 groups of 5 participants):

SubGroup 1 (n=5): +4h, +72h SubGroup 2 (n=5): +5h, +48h SubGroup 3 (n=5): +2h, +8h SubGroup 4 (n=5): +1h, +8h SubGroup 5 (n=5): +3h, +72h SubGroup 6 (n=5): +4h, +24h SubGroup 7 (n=5): +3h, +7h SubGroup 8 (n=5): +2h, +48h SubGroup 9 (n=5): +5h, +7h

For Arm 3 (10 groups of 5 participants), (albendazole + ivermectin treatment x 3 consecutive days), we follow the same schedules as for Arm 2, but adding predose on Day 2 and starting the extractions from that point, as follows

SubGroup 1 (n=5): predose Day 2, +4h, +72h SubGroup 2 (n=5): predose Day 2, +5h, +48h SubGroup 3 (n=5): predose Day 2, +2h, +8h SubGroup 4 (n=5): predose Day 2, +1h, +8h SubGroup 5 (n=5): predose Day 2, +3h, +72h SubGroup 6 (n=5): predose Day 2, +4h, +24h SubGroup 7 (n=5): predose Day 2, +3h, +7h SubGroup 8 (n=5): predose Day 2, +2h, +48h SubGroup 9 (n=5): predose Day 2, +5h, +7h SubGroup 10 (n=5): predose Day 2, +1h, +24h

Global Health

Sensitivity analysis populations

ISGIODAI Barcelona Institute for

Safety sensitive populations: A per-protocol analysis will be performed including all randomized participants who received at least one dose of medication.

Efficacy sensitive population: A per-protocol analysis will be conducted, including all randomized participants who received at least one dose of medication, did not withdraw, without major protocol deviations, and were not lost to follow-up. Also, participants who did not meet the inclusion or exclusion criteria, received an incorrect treatment, or were administered an incorrect dose will be excluded from the per-protocol analysis.

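### Phase II is allocated by simple randomisation, which does not deliver the arm sizes of 26/50/50 on which the PK sampling subgroups are built

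*SAP*

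**What the plan says.** SAP 3.4 states the method, the probabilities and the arm sizes together: "participants will be allocated by simple randomization to one of the three study arms with unequal probability (ALB: p=0.2, n=26", followed by a probability of 0.4 and a size of 50 for each of the two FDC arms. Protocol 4.1, under Method of Allocation, names the same method without a ratio: "participants will be allocated by simple randomization to one of the three study arms". In both documents the text then turns to phase III and specifies permuted blocks there, so the two methods are distinguished. The Protocol synopsis gives the same 0.2/0.4/0.4 and 26/50/50.

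Enrolment runs in sequence through three weight groups: "Group 1 (23-<30 kg) 38 participants, group 2 (30-45 kg) 38 participants and group 3 (15-23 kg) 50 participants".

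The PK plan in SAP 4.1 takes the arm sizes as given ("26 in arm 1, and 50 in the arms 2 and 3") and divides each arm into subgroups with assigned sampling times: "5 subgroups of 4 participants + 2 subgroups of 3 participants" for ALB, "For Arm 2 (10 groups of 5 participants" and "For Arm 3 (10 groups of 5 participants". SAP Table 4 and Protocol Table 2 carry 26/50/50 into the *T. trichiura* total.

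Protocol 6.1.2 instead has phase II participants allocated to the three arms with the same chance. That conflicts with the synopsis and with SAP 3.3 and 3.4.

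**The concern.** Under simple randomisation each child is an independent draw, so arm sizes are random. The plan uses them as if they were fixed. If an FDC arm ends at 44, some PK sampling-time pairs are short; if it ends at 56, six children have no assigned subgroup. Within a weight group the ALB children are the only concurrent reference when adverse events are described, and chance alone decides how many there are. Nothing in either document fixes arm counts per weight group in phase II.

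**Working it through.** **Inputs.** N = 126; p = 0.2/0.4/0.4; stated arm sizes 26/50/50; weight groups 38, 38 and 50 (SAP 3.4). PK subgroups from SAP 4.1. Evaluable *T. trichiura* sample 116/223/223, of which 93/178/178 in phase III; 10% loss; cure rates 23.7%, 43.7% and 59%; alpha 0.05/3 = 0.0167, two-sided (SAP 3.5, Tables 3 and 4, and 5.7).

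**1. Reproducing the plan's figures.** 20% of 116 is 23.2 and 20% of 223 is 44.6, giving 23/45/45. Dividing by 0.9: 23/0.9 = 25.6, so 26; 45/0.9 = 50. Sum 126. The PK subgroups match: 5×4 + 2×3 = 26 and 10×5 = 50. The two-proportion power formula with 116/223/223 gives 90.6%, 100.0% and 80.2%, against the stated 91%, 100% and 80%.

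**2. Arm sizes under simple randomisation.** Counts follow a multinomial(126; 0.2, 0.4, 0.4) distribution. Each arm is binomial with mean Np and SD √(Np(1−p)); ranges below are the 2.5th to 97.5th percentiles.

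| Arm | Stated | Mean | SD | 95% range |
|---|---|---|---|---|
| ALB | 26 | 25.2 | 4.5 | 17–34 |
| each FDC arm | 50 | 50.4 | 5.5 | 40–61 |

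Summing the multinomial over all splits:
- both FDC arms reach 50: 20.6%, so at least one falls short 79.4% of the time;
- ALB below 26: 53.5%;
- all three arms within 2 of the stated size: 12.2%;
- both FDC arms at least 40, which is 4 per subgroup on average: 95.5%.

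**3. Within a weight group.** ALB in a group of 38 is binomial(38, 0.2): mean 7.6, 95% range 3–13. In the group of 50 it is 5–16. P(ALB ≤ 4 of 38) = 9.9%; for at least one of the two such groups, 1 − (1 − 0.0986)² = 18.7%. P(ALB ≤ 2 of 38) = 1.1%.

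**4. Effect on pooled power.** Analysed n = phase III n plus 0.9 × the phase II count, with the two FDC arms held equal:

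| Phase II ALB / each FDC | Analysed ALB / each FDC | ALB vs FDC | FDC vs FDCx3 |
|---|---|---|---|
| 16 / 55 | 107 / 228 | 88.9% | 81.2% |
| 26 / 50 | 116 / 223 | 90.6% | 80.2% |
| 34 / 46 | 124 / 219 | 91.7% | 79.4% |

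Unequal FDC arms change little either. Phase II counts of 40 and 60 give 178 + 36 = 214 and 178 + 54 = 232, with harmonic mean 2×214×232/446 = 222.6 against 223.

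**5. If the equal allocation of Protocol 6.1.2 were followed,** the expected split would be 42/42/42, far from what the PK table needs.

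**The case against.** The strongest reply is that little depends on exact counts. Most of it stands.

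- **Escalation.** A reader might infer that too few ALB children would undermine the DSMB's decision on each weight group. The documents do not support this. The rule in Protocol 3 and SAP 3.6 is an absolute count of serious adverse reactions or SUSARs, and Protocol 4.1 ties clearance to that rule. Nor would 8 controls support a formal comparison: with assumed adverse event rates of 10% and 30%, Fisher's exact test on 8 versus 30 children has about 7% power (about 26% for 10% and 40%).
- **PK.** A reader might infer that the PK analysis fails without full subgroups. SAP 4.1 describes sparse population sampling, which tolerates uneven subgroups. No minimum is stated, and the full PK plan is a separate document that is not available here.
- **The exact split.** P(exactly 26/50/50) is 0.69%, but no single split can exceed about 0.70%. The figure says nothing about harm.
- **Wording.** Simple may be a loose term for unblocked, since Protocol 6.3 mentions a list prepared in advance. That is possible, but no passage says so, and the contrast with blocks for phase III favours the literal reading. Either way the text needs correcting.
- **Predictability.** Simple randomisation is the least predictable method, and phase II is open label at one site. This is a genuine cost of any fixed list.

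What remains is that the stated method and the stated sizes do not fit together, and the PK table has no provision for other sizes.

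**Conclusion.** The inconsistency is real and worth correcting, with modest consequences. Taken literally, the plan leaves at least one FDC arm short of its PK table about 79% of the time and lets ALB fall anywhere from 3 to 13 in a 38-child group. The harm is confined to uneven or unfilled sampling-time subgroups and thin concurrent controls for descriptive safety. It does not extend to the escalation rule, to the validity of a population PK model or, beyond one or two percentage points, to pooled efficacy power. The figures assume independent draws at 0.2/0.4/0.4, exactly 126 randomised, and 10% loss in every arm for the power check.

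**What to change.** Replace simple randomisation in SAP 3.4 and Protocol 4.1 with one random permutation per weight group:

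| Weight group | ALB | FDCx1 | FDCx3 |
|---|---|---|---|
| 1 (38) | 8 | 15 | 15 |
| 2 (38) | 8 | 15 | 15 |
| 3 (50) | 10 | 20 | 20 |
| Total (126) | 26 | 50 | 50 |

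Write the counts out. Because 38 is not a multiple of 5, ordinary 1:2:2 blocks of five cut off at 38 would give the exact totals only 18% of the time, although always within 2 per arm.

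Keep assignment central and concealed, and withhold the per-group counts from recruiting staff. State how participants replaced under Protocol 7.2 take list positions; without this, a fixed list does not guarantee the treated numbers. Reconcile Protocol 6.1.2 with the synopsis and SAP 3.3 and 3.4.

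**Cost.** No extra participants, visits or analyses. The last few allocations in each weight group become slightly more predictable, which matters somewhat in an open-label, single-site phase. The list also does not balance PK subgroups within a weight group, since 15 does not divide by 10 nor 8 by 7; subgroup assignment has to run across the weight groups.
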